#### 14.3.2. Primary and Secondary Efficacy Analysis

Primary and secondary efficacy analyses will be based on the ITT population, those patients that are symptomatic with bi-allelic deletion mutations of *SMN1* and 2 copies of *SMN2* without the *SMN2* gene modifier mutation (c.859G>C). These analyses are to test the superiority of AVXS-101 to the results from natural observation study (PNCR) [21].

The first co-primary efficacy hypothesis to be tested is:

$$\begin{aligned} \mathbf{H}_0: p_{AVXS-101} &= 0.1\% \\ &\textit{versus the alternative} \\ \mathbf{H}_a: p_{AVXS-101} &> 0.1\%, \end{aligned}$$

where  $p$  is the proportion of functional independent sitting for at least 30 seconds at the 18 months of age study visit.

The second co-primary efficacy hypothesis to be tested is:

$$\begin{aligned} \mathbf{H}_0: p_{AVXS-101} &= p_{HISTORICAL-FINKEL} \\ &\textit{versus the alternative} \\ \mathbf{H}_a: p_{AVXS-101} &\neq p_{HISTORICAL-FINKEL}, \end{aligned}$$

where  $p$  is the proportion surviving at 14 months of age.

Primary efficacy endpoints will be examined on the ITT population. Testing for the first co-primary endpoint, functional independent sitting will first be performed using 1-sided exact binomial test. Only if the null hypothesis of equality in proportion of functional independent sitting is rejected at  $p < 0.025$ , will the co-primary endpoint survival improvement be tested using 2-sided Fisher's Exact test on the ITT population, comparing to matched patients from natural observational study (PNCR). This hierarchy approach strongly protects the Type I error rate.

The hypothesis for both co-secondary efficacy endpoints to be tested is:

$$\begin{aligned} \mathbf{H}_0: p_{AVXS-101} &= 0.1\% \\ &\textit{versus the alternative} \\ \mathbf{H}_a: p_{AVXS-101} &> 0.1\%, \end{aligned}$$

where  $p$  is the proportion of patients maintaining the ability to thrive/are independent of ventilatory support.

One-sided exact binomial tests will be executed for secondary efficacy analyses on the ITT population.

A sensitivity analysis will be conducted by repeating the primary efficacy analysis on the efficacy completers analysis population.

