### 8.2. Patient Exclusion Criteria

Patients must not meet any of the following exclusion criteria:

1. Previous, planned or expected scoliosis repair surgery/procedure during the study assessment period
2. Pulse oximetry < 96% saturation at screening while the patient is awake or asleep without any supplemental oxygen or respiratory support, or for altitudes > 1000 m, oxygen saturation < 92% awake or asleep without any supplemental oxygen or respiratory support  
Pulse oximetry saturation may decrease to < 96% after screening provided that the saturation does not decrease by  $\geq 4$  percentage points
3. Tracheostomy or current use or requirement of non-invasive ventilatory support averaging  $\geq 6$  hours/day over the 7 days prior to the screening visit; or  $\geq 6$  hours/day on average during the screening period or requiring ventilatory support while awake over the 7 days prior to screening or at any point during the screening period prior to dosing
4. Patients with signs of aspiration/inability to tolerate non-thickened liquids based on a formal swallowing test performed as part of screening. Patients with a gastrostomy tube who pass the swallowing test will be allowed to enroll in the study

5. Patients whose weight-for-age is below the third percentile based on World Health Organization (WHO) Child Growth Standards [26]
6. Active viral infection (includes human immunodeficiency virus [HIV] or positive serology for hepatitis B or C, or Zika virus)
7. Serious non- respiratory tract illness requiring systemic treatment and/or hospitalization within 2 weeks prior to screening
8. Upper or lower respiratory infection requiring medical attention, medical intervention, or increase in supportive care of any manner within 4 weeks prior to screening
9. Severe non-pulmonary/respiratory tract infection (e.g., pyelonephritis or meningitis) within 4 weeks before administration of gene replacement therapy or concomitant illness that, in the opinion of the Principal Investigator, creates unnecessary risks for gene replacement therapy such as:
  - a. Major renal or hepatic impairment
  - b. Known seizure disorder
  - c. Diabetes mellitus
  - d. Idiopathic hypocalcuria
  - e. Symptomatic cardiomyopathy
10. Known allergy or hypersensitivity to prednisolone or other glucocorticosteroids or their excipients

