Based upon the widely cited natural history of the disease (Pediatric Neuromuscular Clinical Research Network [PNCr]) [*Neurol.* 2014; 83(9):810-817], it is expected that no patients in this population would be expected to attain the ability to sit without support or accomplish other milestones (rolling over, standing, walking) prior to 18 months of age. Assuming that the true response rate for the primary endpoint is actually zero (or as low as 0.1%) in the population of interest of the historical control, the first co-primary efficacy endpoint hypothesis:

$$\begin{aligned} H_0: p_{AVXS-101} &= 0.1\% \\ &\text{versus the alternative} \\ H_a: p_{AVXS-101} &> 0.1\%, \end{aligned}$$

where  $p$  is the proportion of functional independent sitting for at least 30 seconds at the 18 months of age study visit.

Based upon preliminary results from the ongoing Phase 1 clinical study AVXS-101-CL-101, at least 40% of treated symptomatic patients with bi-allelic deletions of *SMN1* and 2 copies of *SMN2* without the *SMN2* gene modifier mutation (c.859G>C) are expected to achieve the co-primary efficacy endpoint of functional independent sitting for at least 30 seconds at the 18 months of age study visit. With the assumption for the true response rate of AVXS-101 for the

primary endpoint being in the range of 30% - 40%, a sample size of 15 patients that meet ITT criteria will be enrolled and assuming approximately 30% of patients are excluded from analysis, would yield an ITT population that would provide power of > 90% to detect a significant difference from 0.1% with  $\alpha = 0.025$  using a 1-sided exact test for a binomial proportion.

The second co-primary efficacy endpoint hypothesis:

$$H_0: p_{AVXS-101} = p_{HISTORICAL-FINKEL}$$

*versus the alternative*

$$H_a: p_{AVXS-101} \neq p_{HISTORICAL-FINKEL}$$

where  $p$  is the proportion of patients surviving at 14 months of age.

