Based upon preliminary results from the ongoing Phase 1 clinical study AVXS-101-CL-101, at least 80% of treated symptomatic patients with bi-allelic *SMN1* deletions and 2 copies of *SMN2* without the *SMN2* gene modifier mutation (c.859G>C) are expected to achieve the co-primary efficacy endpoint of survival through 14 months of age. It is anticipated that 75% of patients in the PNCR population would not survive beyond 13.6 months of age, and that these control patients will represent a 25% survival rate based upon the natural history of the disease. With this efficacy, an enrolled sample size of 15 patients that meet ITT criteria (assuming 30% of patients are excluded from the analysis) would yield an ITT population that would provide power of > 80% to detect a significant difference from the historical control with  $\alpha = 0.05$  using a 2-sided Fisher's Exact test, comparing to the 26 age and gender matched patients from a published natural history observational study performed at 3 large, tertiary care centers in the United States (Harvard University, Columbia University, Children's Hospital of Philadelphia; PNCR).

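### The 0.1% null for ability to thrive and ventilator independence is borrowed from sitting without support, and one success among 15 children is enough to reject it

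*Protocol*

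**What the plan says.** The co-secondary endpoints, defined in the Synopsis and section 6.2, are both assessed at 18 months of age. Thriving means tolerating thin liquids, weighing above the third percentile and needing no mechanical or non-oral feeding. Ventilator independence means no daily ventilator use.

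Section 14.3.2 writes "The hypothesis for both co-secondary efficacy endpoints to be tested is" H0: p = 0.1% against p > 0.1%, where p "is the proportion of patients maintaining the ability to thrive/are independent of ventilatory support". It adds: "One-sided exact binomial tests will be executed for secondary efficacy analyses on the ITT population". It also says that the primary and secondary analyses test superiority to the PNCR natural-history study. Section 14.3.1 names that study as comparator only for sitting and survival.

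The reasoning behind 0.1% is in the Synopsis (Statistical Methods) and section 14.2. Section 14.2 expects that "no patients in this population would be expected to attain the ability to sit without support or accomplish other milestones", and words the 0.1% assumption for the primary endpoint.

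For survival, section 14.2 does use a natural-history rate: "these control patients will represent a 25% survival rate based upon the natural history of the disease", with 13.6 months of age as the reference point.

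This is protocol version 2.0, the latest text of section 14.3.2 available. Version 1.0 sets the same null.

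**The concern.** In a single-arm study the null value is the only comparator. An almost-zero null suits a milestone that untreated children are said never to reach. Thriving and ventilator independence are different in kind, because many children can have much of the success state at entry and lose it later. Section 8.2 excludes "Patients with signs of aspiration/inability to tolerate non-thickened liquids based on a formal swallowing test performed as part of screening", children below the third weight percentile, and children needing ventilation for 6 or more hours a day or at all while awake. The question for these endpoints is how many untreated children would still qualify at 18 months, and the protocol gives no figure.

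If that rate is even a few percent, rejecting 0.1% does not separate a drug effect from untreated persistence. The co-secondary objectives ask for exactly that separation, and the plan would report a rejection as superiority over natural history.

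**Working it through.** **Inputs.** From sections 14.2 and 14.3.2: null 0.1%; one-sided exact binomial test; 15 ITT patients with about 30% excluded, so 15 × 0.70 = 10.5, that is 10 or 11 evaluable. Section 14.3.2 states 0.025 for sitting and no level for the co-secondary tests; 0.025 is assumed for them here.

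**The plan's own figure.** One success rejects 0.1% at n = 10, 11 or 15, so power for sitting is 1 − (1 − p)^n.
- n = 10: 1 − 0.7^10 = 97.2% at a true 30%, and 1 − 0.6^10 = 99.4% at 40%.
- n = 11: 98.0% and 99.6%.
- n = 15: 99.5% and 99.95%.

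The stated power above 90% is reproduced. The protocol states no power for the co-secondaries.

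**Successes needed on the co-secondaries.** P(X ≥ 1) under p = 0.001 is 1 − 0.999^n:
- n = 15: 0.0149
- n = 11: 0.0109
- n = 10: 0.0100

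All are below 0.025, so one success is enough. If 0.025 were split into 0.0125 for each endpoint, 15 patients would need two successes, but one would still suffice with 12 or fewer.

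**When the level holds.** With a one-success rule, solve 1 − (1 − p)^15 = 0.025. This gives p = 1 − 0.975^(1/15) = 0.17%. The exact 95% confidence interval for 1/15 accordingly runs from 0.17% to 31.9%. Against a 1% null, one success in 15 gives p = 0.140.

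**Chance that an ineffective product rejects.** The untreated 18-month rate is not in the documents, so a range is assumed. The chance is 1 − (1 − p)^n.

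| Assumed untreated rate | n = 15 | n = 11 | n = 10 |
|---|---|---|---|
| 1% | 14.0% | 10.5% | 9.6% |
| 2% | 26.1% | 19.9% | 18.3% |
| 5% | 53.7% | 43.1% | 40.1% |
| 10% | 79.4% | 68.6% | 65.1% |

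**What a different null would require at one-sided 0.025.** For ventilator independence, no daily ventilator use at 18 months implies being alive and not permanently ventilated at that age. The 25% assumed for 13.6 months can therefore serve as an upper bound.

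| n | Rule against 25% | Exact size | Power at true 80% | Power at true 60% |
|---|---|---|---|---|
| 15 | at least 8 | 1.7% | 99.6% | 79% |
| 11 | at least 7 | 0.8% | 95% | 53% |
| 10 | at least 6 | 2.0% | 97% | 63% |

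One success fewer exceeds 0.025 each time: 0.057 for 7/15, 0.034 for 6/11 and 0.078 for 5/10. As illustrations for thriving with 15 patients, a 5% null needs 4/15 (size 0.5%) and a 10% null needs 5/15 (size 1.3%).

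**The case against.** The strongest reply is that the true untreated rates may be close to zero. Section 5.1 describes progressive weakness and death from respiratory failure before 2 years of age. A reader might infer that the protocol's own figures refute 0.1%, and they do not. The 25% is survival at 13.6 months without death or permanent ventilation. A child on 10 hours a day of non-invasive support with a feeding tube counts as a survivor there and fails both co-secondaries. Section 5.2 reports that 88 of 94 two-copy patients lived less than 21 months; the other 6 (6.4%) are bare survivors, with nothing said about feeding or ventilation. Nor are these purely states to be kept. Section 8.2 admits children on less than 6 hours a day of ventilation while asleep, and children with a gastrostomy who pass the swallowing test, so some may enter already failing an 18-month definition. All of this stands, and it is why the value is called unsupported rather than contradicted.

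Two further readings should be resisted. The 25% does not bound the thriving rate, because that definition says nothing about ventilation. And the lack of a stated level or testing order for the co-secondaries is not a fault in itself: the sentence on Type I error protection in section 14.3.2 concerns the two co-primaries, and the rest may be in the SAP.

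None of this supplies a basis for 0.1%. A rationale might exist in the SAP or in a later protocol version, neither of which was available.

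**Conclusion.** The concern holds. The protocol fixes a 0.1% null for two endpoints for which it offers no natural-history rate, and the resulting rule is one success in 15 (6.7%), or one in 10 or 11 after the planned exclusions. The nominal level is kept only if the untreated rate is at most about 0.17% with 15 patients. Between assumed untreated rates of 1% and 10%, the chance of a false rejection is 14% to 79%. These percentages rest on assumed rates, a one-sided 0.025 level and 15 evaluable patients; the one-success rule does not depend on the assumed rates.

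It would be too strong to say that one child proves the product works. One success rejects one secondary null, and the efficacy claim rests on the co-primaries. The point is therefore one that should be fixed, not one that undermines the trial's main conclusion.

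**What to change.** Replace 0.1% in section 14.3.2 separately for each co-secondary endpoint.

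- **Preferred:** use the 18-month proportion, or its upper confidence limit, from the natural-history data already planned for the survival comparison, if those data record the item. The protocol does not show that they hold swallowing, weight or daily ventilator data, so this must be checked first.
- **Ventilator independence, if no rate is available:** use 25% as an upper bound, with the rules of at least 8/15, 7/11 or 6/10 shown above.
- **Thriving, if no rate is available:** state and justify a conservative null of its own.
- **If no null can be justified:** report the proportions with exact confidence intervals and make no superiority claim.

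The cost is protocol and SAP wording and, where the data allow, one extraction. The secondary claims become harder to win. Against 25%, power at a true rate of 60% is 79% with 15 patients but only 63% or 53% with 10 or 11, so the revised text should give power at the evaluable number as well.

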### 14.2. Sample Size Calculation

This is a pivotal Phase 3, open-label, single-arm, single-dose, study assessing the efficacy and safety of AVXS-101 (gene replacement therapy) in up to twenty (20) patients with spinal muscular atrophy (SMA) Type 1 who meet enrollment criteria, may be either symptomatic or pre-symptomatic and are genetically defined by no functional survival motor neuron 1 gene (*SMN1*) with 1 or 2 copies of survival motor neuron 2 gene (*SMN2*) and who are < 6 months (< 180 days) of age **at the time** of gene replacement therapy (Day 1). Enrolling up to twenty (20) patients under the broader enrollment criteria is projected to enable enrollment of at least fifteen (15) patients that meet the Intent-to-Treat Population (ITT) criteria. The ITT population is identified as symptomatic patients with bi-allelic *SMN1* deletions and 2 copies of *SMN2* without the *SMN2* gene modifier mutation (c.859G>C) and will comprise the primary population for evaluation of the primary and secondary endpoints. Study power is based upon efficacy analysis of the ITT population. Furthermore, the first three patients enrolled must meet criteria for the Intent-To-Treat Population to enable a comparison of CHOP-INTEND scores at one-month following gene replacement therapy to enable a comparison of patient response between AVXS-101-CL-303 patients and Cohort 2 patient results from the Phase 1 trial (AVXS-101-CL-101). Patients with 1 copy of *SMN2*, pre-symptomatic patients and patients with the *SMN2* gene modifier mutation (c.859G>C) and other permutations outside of those specified in the ITT population will be evaluated separately as part of additional subgroup analyses. Details of all analyses will be contained within the Statistical Analysis Plan.

The two co-primary efficacy endpoints will be assessed in sequence: The endpoint of functional independent sitting will be assessed first and, only if this assessment meets statistical significance will the endpoint of survival be assessed.

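### The two co-secondary endpoints have formal superiority tests outside the testing sequence that protects the co-primaries, with a modest rise in the chance of a false efficacy claim

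*Protocol*

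**What the plan says.** The references are to protocol version 2.0, the latest body text available. The file opens with the end of a later list of changes, so a later version may exist; the part of that list shown does not touch this point.

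- Section 14.2: "The two co-primary efficacy endpoints will be assessed in sequence", with sitting first. The sitting test has alpha 0.025, "using a 1-sided exact test for a binomial proportion". Survival uses a two-sided Fisher's exact test at 0.05.
- Section 14.3.2 repeats the gate: "Only if the null hypothesis of equality in proportion of functional independent sitting is rejected at" one-sided 0.025 is survival tested. The paragraph ends: "This hierarchy approach strongly protects the Type I error rate".
- The same section continues: "The hypothesis for both co-secondary efficacy endpoints to be tested is", followed by a null rate of 0.1% and a one-sided alternative for both ability to thrive and ventilator independence. It closes the topic with "One-sided exact binomial tests will be executed for secondary efficacy analyses on the ITT population".

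No condition, order, alpha or adjustment is given for these last two tests. Section 14.3.2 introduces the primary and secondary analyses together as tests of superiority over natural history. Section 14.1.2.3 calls the All Enrolled analyses descriptive; the co-secondary tests carry no such label.

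**The concern.** Four formal efficacy tests are laid down, and the order of testing governs two of them. Read literally, nothing prevents a co-secondary being declared significant after sitting has failed and survival has, for that reason, not been tested. Nor does anything prevent one being claimed after survival has failed, or one co-secondary being claimed without the other.

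In a single-arm pivotal trial, a significant co-secondary could then be offered in support of efficacy where the sequence would have stopped, and it would not share the error control that the section claims for its hierarchy. The point is the missing link between the tests. Whether 0.1% is a sensible null for the co-secondaries is a separate matter.

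**Working it through.** **Inputs.** Section 14.2: 15 enrolled patients meeting ITT criteria, about 30% excluded (15 × 0.7 = 10.5, so 10 or 11 analysed), true sitting rate 30% to 40%, survival 80% against 25% with 26 controls. Section 14.3.2: 0.1% null for sitting and both co-secondaries.

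**The plan's own power figures.** One responder rejects the 0.1% null at one-sided 0.025 for any n up to 25, since 1 − 0.999^25 = 0.0247. Sitting power at n = 10 is 1 − 0.7^10 = 97.2% and 1 − 0.6^10 = 99.4%, so the stated figure of more than 90% reproduces. Survival power by full enumeration of the Fisher test is 81.9% (n = 10), 85.9% (n = 11) and 92.6% (n = 15), so more than 80% reproduces.

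**Size of one 0.1%-null test.** s = 1 − 0.999^n, which is 1.00% (n = 10), 1.09% (n = 11) and 1.49% (n = 15). The unstated alpha does not matter here: one responder rejects at 0.025 and at 0.05 alike.

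**All nulls true.** Three tests have no gate before them: sitting, thrive and ventilator independence. Under independence the chance of at least one false claim is 1 − (1 − s)³. For positive dependence I used a common Gaussian correlation between the three test statistics; the correlations are assumptions.

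| Analysed | Correlation 0 | 0.5 | 0.8 |
|---|---|---|---|
| 10 | 3.0% | 2.6% | 2.1% |
| 11 | 3.2% | 2.9% | 2.3% |
| 15 | 4.4% | 3.9% | 3.0% |

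Whatever the dependence, the Bonferroni bound 3s limits the figure to 2.99%, 3.28% and 4.47% at n = 10, 11 and 15.

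**Sitting works, the other three nulls hold.** Survival is then tested as well. With 25% survival in both groups, the Fisher test rejects in the favourable direction with probability 1.66% (n = 10) and 1.35% (n = 15). Under independence:

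- n = 10: 1 − (1 − 0.01656)(1 − 0.00996)² = 3.6%
- n = 15: 1 − (1 − 0.01351)(1 − 0.01490)² = 4.3%

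**After the fix.** In a full fixed sequence, a false claim requires rejecting the first true null in the order. Each step is run at no more than 2.5% in the favourable direction, so the familywise error in that direction is at most 2.5%, whatever the dependence.

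**The case against.** The strongest objection is that this rests on what the protocol does not say. Section 14 opens by calling itself a summary of key aspects and sends further detail to an SAP, which was not available here and could supply a gate. Multiplicity for secondary endpoints is often left there. This stands in part: a reader might infer that the protocol directs co-secondary testing whatever the co-primaries show, but it nowhere says so. That is only the effect of an absent condition. It does not dispose of the point, because Section 14.3.2 itself fixes the hypotheses, test, sidedness and population for the co-secondaries, and the general deferrals to the SAP do not mention multiplicity.

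A second objection is that the Type I sentence is not wrong. This stands. The sentence follows the two co-primary steps and precedes the co-secondary hypotheses, and for those two steps it is true. A reader might take it as a false claim about all four tests; its position does not support that.

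Third, the excess is small. This also stands. All three ungated endpoints are measured at 18 months of age in the same children, so positive correlation is likely, and at 10 or 11 analysed a correlation of 0.8 brings the error below 2.5%. Sitting power is at least 97% under the plan's assumptions, so a co-secondary claim after a failed sitting test is remote. A failed survival test is less so.

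**Conclusion.** The point holds in a limited form. The sequence and its error protection cover the two co-primaries correctly. The two co-secondaries have formal one-sided superiority tests with no stated condition, order or alpha, and so fall outside that protection.

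With all nulls true, the error is 3.0% to 4.4% at 15 analysed and about 2.1% to 3.2% at the planned 10 or 11, so at the planned size the excess over 2.5% can vanish. With sitting effective and the other three nulls true, it is 3.6% to 4.3% under independence. These figures rest on the plan's 0.1% nulls, the assumed correlations and, for survival, a common 25% rate.

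A reader might infer 7.3%, from three independent tests at 0.025: 1 − 0.975³. That cannot arise here, because each 0.1%-null test has a size of only 1.0% to 1.5% and the survival test about 1.4% to 1.7% in the favourable direction. Nothing here undermines either co-primary. It is a cheap improvement of minor to moderate importance.

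**What to change.** In Section 14.3.2, extend the fixed sequence to all four tests:

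1. sitting, one-sided 0.025;
2. survival, two-sided 0.05, in the favourable direction;
3. ability to thrive, one-sided 0.025;
4. ventilator independence, one-sided 0.025.

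Formal testing stops at the first non-rejection, and later p-values are reported as descriptive. The order of steps 3 and 4 follows the protocol's own listing. Place the Type I sentence after the full sequence, and mirror the text in the SAP.

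The cost is about two sentences, with no new patients or data and no change in power for either co-primary. The downside is that a co-secondary claim is lost whenever survival is not significant. Under the plan's assumptions that happens with probability 1 − 0.926 = 7% (15 analysed) to 1 − 0.819 = 18% (10 analysed).
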